Measurement time and people in charge of evaluation:

For each criterion, this information is given in the table above.

Generally speaking, the assessment of performance and safety criteria begins with the root canal obturation.

Method of evaluating the efficacy rate of initial or repeat endodontic treatment (at 6 months, 12 months and 24 months for the 2 arms; and 3.5 years and 5 years for the PA1704 arm):

Therapeutic efficacy is a composite criterion based on the radiological data assessed **in blind conditions** by reviewers AND on the clinical data assessed **in an open-label manner** by the investigator at the follow-up visits at 6 months, 12 months, 24 months, 3.5 years and 5 years (only the PA1704 arm for the last 2 visits). With regard to the blind evaluation of the radiological criteria by two independent reviewers, the following clarifications are provided:

- The reviewers shall examine the anonymized retro-alveolar images (JPEG files as described in the imaging procedure in section "Equipment to be used to evaluate clinical trial variables and arrangements for monitoring maintenance and calibration." of this chapter) and answer the following questions:
 - Apical lesion: 1) Presence, absence or appearance of a lesion compared with the TO reference image? 2) In the case of a pre-existing lesion at TO, what is the evolution of the size of the lesion (reduction, stabilization or increase)?
 - Root canal filling density: 1) Is the radiopacity sufficient? 2) Presence of at least one bubble in the filling material?
 - Resorption of extruded material where applicable: Is the extruded material still present in the apical space?
- Timetable: 5 centralized image review campaigns are planned, one before each statistical analysis:
 - o 1st review campaign: At the end of the 6-month follow-up of all enrolled patients, a blind review of the T0 reference image and the 6-month follow-up image,
 - o ^{2nd} campaign: after 12 months' clinical follow-up of all patients, blind review of the 12-month check-up image,
 - o 3rd campaign: After 24 months of clinical follow-up for all patients, a blind review of the 24-month check-up image,
 - 4th campaign: After approximately 3.5 years of clinical follow-up of the patients treated with the PA1704 MD, a centre-blind review of the 3.5-year follow-up image,

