If the patient is seen for treatment outside the protocol (routine care) or for any emergency, the investigator shall collect all the information relevant to the trial (date of consultation, reason for consultation, occurrence of AEs, etc.).

V3 — Clinical follow-up visit at 6 months (± 1 month) — Standard practice

- **Clinical examination**: Verification of the functional status of the treated tooth and percussion test (lateral and axial),
- Recording of AEs.
- Retro-alveolar X-ray check to evaluate the results of endodontic treatment at 6 months: 1) density of the root canal filling (radiopacity + presence of voids), 2) progress of resorption of the extruded material

where appropriate, **3)** apical lesion (absence/appearance/still present compared with T0) and progress of the size of an existing lesion (reduction, stabilization or increase).

Upload the 6-month follow-up retro-alveolar image to the eCRF (reminder: the entire tooth – from the *crown to the apex, including the root* – must be visible in the image; see chapter 6.1).

— The investigator shall evaluate the efficacy of the endodontic treatment on the basis of the clinical and radiological criteria identified (*Note: Only the evaluation of the radiological criteria by the independent reviewers will be taken into account for the primary evaluation criterion (PEC); the investigator's evaluation is to be used to determine further clinical follow-up*).

Procedure in the event of the appearance of a lesion or an increase in the size of a pre-existing lesion:

- If the investigator considers it to be an emergency (e.g. if the tooth is symptomatic and/or non-functional): the investigator will notify the patient of the failure of the endodontic treatment and schedule retreatment. In this case, the patient leaves the trial early due to the failure of the treatment and continues endodontic treatment outside the trial (end-of-trial form to be completed in the eCRF). Performance and safety evaluations now end. Failure notified at 6 months is carried forward as the PEC value (response at 24 months = failure). The patient will not be replaced.
- If the investigator considers that it is NOT an emergency (e.g. if the tooth is asymptomatic): medical advice should be sought from the trial coordinator (who will review the X-rays) before considering retreatment and early discharge from the trial for treatment failure.

V4 — Clinical follow-up visit at 12 months (± 1 month) — Standard practice

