- **Clinical examination**: verification of the functional status of the treated tooth and percussion test (lateral and axial),
- Recording of AEs.
- **Retro-alveolar X-ray check** to evaluate the results of endodontic treatment at 12 months: 1) density of the root canal filling (radiopacity + presence of voids), 2) progress of resorption of the extruded material where appropriate, 3) apical lesion (absence/appearance/still present compared with T0) and progress of the size of an existing lesion (reduction, stabilization or increase).

Upload the 12-month follow-up retro-alveolar image to the eCRF (reminder: the entire tooth – from the *crown to the apex, including the root* – must be visible in the image; see Chapter 6.1).

— The investigator will evaluate the efficacy of the endodontic treatment on the basis of the clinical and radiological criteria identified (*Note: Only the evaluation of the radiological criteria by the independent reviewers will be taken into account for the primary evaluation criterion (PEC); the investigator's evaluation will be used to determine further clinical follow-up*).

Procedure in the event of the appearance of a lesion or an increase in the size of a pre-existing lesion:

- If the investigator considers it to be an emergency (e.g. if the tooth is symptomatic and/or non-functional): the investigator will notify the patient of the failure of the endodontic treatment and schedule retreatment. In this case, the patient leaves the trial early due to the failure of the treatment and continues endodontic treatment outside the trial (end-of-trial form to be completed in the eCRF). Performance and safety evaluations now end. Failure notified at 12 months is carried forward as the PEC value (response at 24 months = failure). The patient will not be replaced.
- If the investigator considers that it is NOT an emergency (e.g. if the tooth is asymptomatic): medical advice should be sought from the trial coordinator (who will review the X-rays) before considering retreatment and early discharge from the trial for treatment failure.

V5 — Clinical follow-up visit at 24 months (± 1 month) — Standard practice

- **Clinical examination**: verification of the functional status of the treated tooth and percussion test (lateral and axial),
- Recording of AEs.

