7.7. Statistical methods

The statistical methods are based on the following elements and will be detailed in the Statistical Analysis Plan.

7.7.1. Sample description:

The description of the subjects enrolled who completed the trial and those enrolled who left prematurely will be presented using a table of absolute (N) and relative (%) frequency. Reasons for premature discharge and deviations from the protocol will be listed.

7.7.2. Descriptive analyses:

Clinical data collected at enrolment and at each visit will be described. Descriptive statistics will be presented according to the nature of the criterion analyzed:

- Quantitative variable: sample size, number of missing data sets, mean, standard deviation, median, minimum and maximum;
- Qualitative variable: absolute frequencies (N) and relative frequencies (%) per class in each group, number of missing data.

Graphs will be provided for each variable.

7.7.3. Comparative analyses:

A comparison of 2 independent means will be made using the Student's t-test; if the variances are unequal (verified by the Fisher's test), use the Welch's test instead of the Student's test. If the conditions for applying the Student test are not met (n < 30), the non-parametric Wilcoxon test is used.

2 independent percentages are compared using Pearson's Chi-2 test. If the conditions for application are not met (at least one theoretical number < 5), Fisher's exact test is used.

7.7.4. Analysis of primary performance criterion:

As a reminder, the primary performance criterion is the efficacy rate at 24 months of treatment based on clinical criteria assessed by the investigator (tooth functionality and pain level) AND radiological criteria assessed blind by independent reviewers (complete healing, reduction of lesions, failure). In the event of failure at 6 or 12 months, the patient will be considered to have failed at 24 months.

The primary criterion will be analyzed using 2 approaches, in accordance with the literature:

- **Primary analysis of soft criteria**: treatment rates with complete or incomplete cure are compared against failure rates;
- **Secondary analysis of strict criteria**: treatment rates with complete healing are compared against rates of failure or incomplete healing (complete healing can take up to 4 or 5 years).

The comparison of efficacy rates between the 2 groups will be carried out using the Dunnett and Gent χ^2 test (Dunnett CW and Gent M 1977; Elie C et al 2008).

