 - o Preoperative pain (symptomatic tooth at enrolment, preoperative VAS).

7.7.11. Handling missing, unused or erroneous data, including drop-outs and withdrawals:

No imputation method is planned. However, as stated above, patients with treatment failure at 6 or 12 months will be withdrawn from the study and will be considered to have treatment failure at 24 months.

7.7.12. Exclusion of certain information from the hypothesis tests, if relevant:

None.

7.7.13. In the case of multi-center investigations, minimum and maximum number of subjects to be included for each center:

Each center will include 22 to 24 patients with an indication for initial or repeat endodontic treatment. The number of repeat treatments may vary between centers, but will total 30% in the sample. Some investigators, because of their specialty in endodontics, will include a majority of patients with an indication for repeat treatment, whereas GP investigators will probably have more indications for first-line treatment.

8. Data management

Procedures for examining data, cleaning databases, issuing and resolving data queries:

See Chapter 6.6, Data quality and monitoring section.

Procedures for verification, validation and securing of the electronic clinical data systems, where applicable:

The data collected in electronic CRFs is recorded directly in an electronic database using ENNOV software and hosted on a secure health data server in accordance with current regulations. The data collected in the paper logbooks is entered by the CRO into the electronic database using ENNOV software.

Data retention:

See the Archiving section in Chapter 12.4.

9. Amendments to the clinical investigation plan

Requests for substantial modifications will be sent by the CRO, on behalf of the sponsor, to the relevant ethics committees for their opinion and to the competent authorities for authorization, in accordance with law 2004-806 of 9 August 2004 and its implementing decrees in force.

Similarly, non-substantial modifications will be sent for information.

An updated version of the amended protocol must be dated. This new version will be sent to the investigators.

The patient information leaflet should be amended if necessary.

10. Deviations from the clinical investigation plan

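### A tooth that leaves the trial for treatment failure between scheduled visits gets no 24-month value and drops out of the main non-inferiority analysis

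*Combined protocol and SAP*

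**What the plan says.** - **When a failure ends participation.** Section 6.3 lists treatment failure needing repeat treatment as a reason for early termination. In the BioRoot RCS arm this applies up to the 24-month follow-up and in the PA1704 arm up to 5 years. It is not tied to a scheduled visit. Section 6.5.2 also foresees unscheduled visits for routine care or emergencies.
- **What is carried forward.** At V3, section 6.5.2 says "Failure notified at 6 months is carried forward as the PEC value (response at 24 months = failure"). At V4 it says "Failure notified at 12 months is carried forward as the PEC value (response at 24 months = failure"). Both sentences sit in the branch for cases that the investigator considers an emergency. In the other branch, "medical advice should be sought from the trial coordinator (who will review the X-rays) before considering retreatment and early discharge from the trial", and there is no carry-forward sentence.
- **Statistics chapter.** Section 7.7.4: "In the event of failure at 6 or 12 months, the patient will be considered to have failed at 24 months". Section 7.7.11: "No imputation method is planned", but "patients with treatment failure at 6 or 12 months will be withdrawn from the study" and scored as failures at 24 months.
- **Analysis sets.** Section 7.6 excludes from PP any patient without the primary criterion, and lists absence of performance data among the major deviations. mITT requires at least one efficacy assessment at 6, 12 or 24 months. Section 7.7.4 makes PP the main analysis set and mITT the check on stability.

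**The concern.** The intention is plainly that a failed tooth counts as a failure. The wording delivers this only for failures at the 6- and 12-month visits. A tooth that fails at, say, month 18 and leaves for retreatment has no 24-month assessment, no carried-forward value and no imputed value. PP then excludes the patient because the primary criterion is missing. The event that the endpoint is meant to count becomes the reason for not counting it.

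In a non-inferiority trial this is not neutral. Removing the same share of failures from both arms pulls two different success rates together. Uneven loss can push the result either way. With few failures expected, one or two teeth matter.

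A second, smaller gap concerns teeth that do not leave. Sections 7.7.4 and 7.7.11 treat every 6- or 12-month failure as final and withdrawn. Section 6.5.2 lets a non-emergency tooth stay after the coordinator's review. If that tooth is read as reduced or healed at 24 months, section 7.7.4 scores it a failure, while nothing in the non-emergency branch of section 6.5.2 overrides the 24-month reading. Two analysts could score it differently.

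**Working it through.** **1. The passages side by side**

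| Exit for failure | Carry-forward rule | 24-month value | PP | mITT |
|---|---|---|---|---|
| Before the 6-month visit | none | none | excluded | excluded: no 6-, 12- or 24-month efficacy |
| At the 6- or 12-month visit | 6.5.2, 7.7.4, 7.7.11 | failure | kept | kept |
| Between 6 and 12, or between 12 and 24 months | none | none | excluded | may be in the set through an earlier assessment, but with no 24-month value and no imputation |

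The supportive mITT analysis therefore does not recover the lost failures.

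**2. The plan's own sample size**

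Inputs from sections 7.2 and 7.3: 90% efficacy in both arms, margin 13 points, one-sided alpha 5%, power 80%.

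n = (1.645 + 0.842)² × (0.9×0.1 + 0.9×0.1) / 0.13² = 65.85, so 66 per group. The plan's figure reproduces. Expected failures per arm are 0.10 × 66 = 6.6, about 7.

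**3. How near the boundary lies (assumed counts)**

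Wald lower limit = d - 1.645 × √[p_N(1-p_N)/n_N + p_R(1-p_R)/n_R], where d = p_N - p_R and p is the success rate. Non-inferiority is shown if the limit is above -13.

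| Failures PA1704 vs BioRoot | d (points) | SE (points) | Lower limit | Shown? |
|---|---|---|---|---|
| 9/66 vs 7/66 | -3.03 | 5.68 | -12.37 | yes |
| 10/66 vs 7/66 | -4.55 | 5.82 | -14.11 | no |
| 9/65 vs 7/66 (one of the 10 dropped) | -3.24 | 5.72 | -12.65 | yes |
| 8/64 vs 7/66 (two of the 10 dropped) | -1.89 | 5.61 | -11.12 | yes |
| 9/66 vs 6/65 (one BioRoot failure dropped from the first row) | -4.41 | 5.54 | -13.52 | no |

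The last row shows that loss in the comparator arm works against PA1704.

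**4. Dependence on the test**

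The plan names the Dunnett and Gent χ² test. Its null estimates are p_R = (successes in both arms + 0.13 n_N)/(n_N + n_R) and p_N = p_R - 0.13. For 10/66 vs 7/66, p_R = (56 + 59 + 8.58)/132 = 0.936 and p_N = 0.806. Observed minus expected PA1704 successes is 56 - 53.21 = 2.79. Summed over the four cells:

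χ² = 2.79² × (1/53.21 + 1/12.79 + 1/61.79 + 1/4.21) = 2.73, with root 1.652 against 1.645.

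So this form already just shows non-inferiority at 10/66 vs 7/66, and gives 1.85 (shown) at 9/66 vs 6/65. At 11/66 vs 7/66 it gives 1.30 (not shown), and with two of those 11 dropped (9/64) 1.90 (shown). The Farrington-Manning statistic is 1.63 at 9/65 vs 7/66, just missed. The boundary moves by about one tooth between forms.

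**5. The same share lost in both arms (assumed shares)**

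At the null boundary (77% vs 90%, 66 per arm), let a share s of failures be dropped. Each success rate becomes p/[p + (1-p)(1-s)].

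| s | PA1704 | BioRoot | Difference (points) | Chance of concluding non-inferiority |
|---|---|---|---|---|
| 0 | 77.0% | 90.0% | -13.0 | 5.0% |
| 10% | 78.8% | 90.9% | -12.1 | 6.7% |
| 20% | 80.7% | 91.8% | -11.1 | 9.1% |
| 30% | 82.7% | 92.8% | -10.1 | 12.7% |

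These are normal approximations.

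**The case against.** **The loss is inferred.** No sentence says that between-visit failures are to be left out; the conclusion comes from reading sections 6.3, 7.6 and 7.7.11 together. Section 7.6 treats off-schedule visits as minor deviations, so an off-schedule failure might be booked against a scheduled visit. Section 7.7 defers detail to a later SAP. This shows that the gap can be closed, not that it is closed. Nothing in the text assigns a month-18 exit to a visit, and an SAP written from this wording would inherit the gap.

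**The figures sit at the boundary.** They do, and they vary with the test. They show sensitivity and do not forecast a reversed result. This part of the objection stands.

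**Three stronger readings that the documents do not support:**

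- *The open-label call contradicts blind assessment.* A reader might infer this because section 6.5.2 says "Only the evaluation of the radiological criteria by the independent reviewers will be taken into account for the primary evaluation criterion (PEC") and then carries forward a failure notified by the investigator. The first statement concerns radiological criteria. The second concerns a tooth sent for retreatment, whose 24-month state can no longer be observed. Counting it as a failure is sound and agrees with the definition of ineffective treatment in section 3.1.2. The 6- and 12-month images are also due for central blind reading (section 6.1: "At the end of the 6-month follow-up of all enrolled patients, a blind review of the T0 reference image", together with the 6-month image).
- *Section 7.7.4 does not say whose reading defines failure.* The sentence just before the rule names the investigator for the clinical criteria and the blind reviewers for radiology.
- *The arm letter in the patient code unblinds the readers.* Section 6.1 has the CRO anonymise the files first and blinds the readers to arm.

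**Conclusion.** The point holds for failure exits outside the 6- and 12-month visits. Followed as written, the plan removes true failures from its main analysis, and no other section repairs this. The conflict over non-emergency teeth that stay is also real but narrower: sections 7.7.4 and 7.7.11 against section 6.5.2.

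The size is unknown, because the documents give no rate of between-visit failure exits. On the assumed counts, one or two lost teeth are enough to change the conclusion near the margin. On assumed losses of 10% to 30% of failures in both arms, the one-sided error rises from 5% to about 6.7% to 12.7%. That second result rests on equal shares being lost when PA1704 is truly worse by the margin. If the true rates are equal, equal shares leave the difference at zero. The point should be fixed before analysis; it does not put the design in question.

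**What to change.** Reconcile sections 6.3, 6.5.2, 7.6, 7.7.4 and 7.7.11 on scoring:

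1. Any tooth that leaves the trial for treatment failure before the 24-month visit, whenever notified, is scored as a failure at 24 months.
2. That score counts as an available primary criterion and as available performance data, so the patient stays in both PP and mITT. The deviation for absent performance data must not exclude such a patient. The other listed major deviations, such as an allocation error or a major enrolment breach, still apply.
3. For teeth called failures at 6 or 12 months that stay in the trial, state one scoring rule, using the composite with the blind radiological reading, before any 24-month data are seen.

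Optional: for failure exits at the 6- or 12-month visit, report by arm how often the investigator's call agrees with the blind reading of the same image. Between-visit exits may have no image and cannot be covered in the same way.

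The cost is protocol and SAP wording, plus one table if the option is taken. It needs no extra visits, images or patients, and patient management is unchanged.
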